## 5.4. Surgery and Delivery System

The Surgery and Delivery System details captured on the eCRFs will be summarized. Individual subject data will be presented in a data listing.

Data from the 1st and 2nd (if applicable) surgical attempt will be summarized separately.

The count and percentage of subjects with surgical deviations will be presented, and individual subjects will be presented in a data listing.

## 5.5. Clinical Laboratory Tests

Clinical laboratory data will be summarized by type of lab test. Descriptive statistics will be presented for each laboratory test at baseline and at each scheduled follow-up time point, and for the change from baseline.

Frequency tabulations of subjects with TE abnormal clinical laboratory results will be presented for each test for each scheduled follow-up time point. TE abnormal low results are defined as those below the laboratory normal range where baseline was not below the normal range low value. TE abnormal high results are those defined as those above the laboratory normal range where baseline was not above the normal range high value. An overall tabulation will also be presented for subjects with at least 1 occurrence of a TE abnormal result at any follow-up time point for that test. A listing of subjects' laboratory results (all results at scheduled and unscheduled time points) will be provided, with flags for TE abnormal results.

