PGIC-Q								x	x	
CGIC								x	x	
Change in concomitant medications				<-----	Continuous----->					
Adverse events				<-----	Continuous----->					
Blood samples volume ⁱ		16.3 mL	0	0	20 mL ^k	16.3mL	10 mL	10 mL	10 mL	16.3 mL

BCVA=Best Corrected Visual Acuity; CGIC=Clinician Global Impression of Change; ETDRS=Early Treatment Diabetic Retinopathy Study; IOP=intraocular pressure; MN Read=Minnesota reading test; NEI-VFQ-25=National Eye Institute Visual Functioning Questionnaire; PGIC-Q=Patient Global Impression of Change – Quality of Life; PGIC-S=Patient Global Impression of Change – Symptoms; SD-OCT=spectral domain optical coherence tomography; SF-36=Short Form (36) Health Survey, FRI= Functional Reading Index questionnaire

Note 1: Screening procedures must occur within 45 days prior to treatment and may occur over multiple days. An additional optional pre-screening visit may be performed to determine potential subject BCVA for eligibility purposes. At the next screening visits, BCVA will be performed twice and the best value (lowest logMAR value) will be used as the subjects' baseline BCVA value.

Note 2: If a subject withdraws early from the Safety Run-in Phase, the end-of-study assessments (described in [Table 2](#)) should be performed.

- a) Subjects will be presented with an optional pre-screening ICF to allow the determination of their BCVA results prior to full study screening. The subjects who meet the BCVA eligibility criteria will be further screened to determine the full study eligibility. For the full study eligibility assessments, the subject will be presented a separate ICF within 45 days prior to treatment. The pre-screening visit is optional
- b) Best Corrected Visual Acuity testing includes BCVA using the ETDRS chart under high illumination and standardized conditions at 4 meters and 1 meter (as needed).
- c) Axial length should be recorded once at screening as a baseline measure. Any instrument may be used OR measurement taken from the subjects medical records may be utilized. Measurement, instrument and date of recording will be noted in the CRF.

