9.1.1.1. Screening Phase

Prior to the full study screening phase, optional BCVA pre-screening may be done to evaluate subjects for BCVA eligibility. In this case, subjects must sign an optional pre-screening ICF prior to testing. The site will determine results of local testing and indicate if the subject is eligible for full study screening. If the BCVA test indicates the subject meets the necessary eligibility criteria, he or she will enter the full screening phase under the full study ICF for determination of full study eligibility.

All subjects will be required to give written informed consent to participate in the trial. In a separate consent, subjects will have the option of providing a DNA sample for genotyping. Subjects will also have the option of donating their eyes for histological evaluation post mortem, using a supplemental informed consent.

After giving written informed consent, subjects may be screened over a period of up to 45 days prior to treatment to assess their eligibility for the study according to the inclusion and exclusion criteria defined for this study. The screening process may occur over a period of days. If a subject fails screening for a reason determined to be temporary, they may be rescreened to determine eligibility by following these criteria:

- Elevated IOP, uncontrolled blood pressure, elevated liver enzymes , decreased platelets and decreased renal function, if correctable with treatment or time
- Acute infections, after successful treatment
- Time-bound restrictions (e.g., Exclusions 8, 9, 12, 20, 21 and 25) after an appropriate waiting period such that the exclusion no longer applies
- Use of prohibited prior medications, after an appropriate waiting period.

Potential patients who fail screening for visual acuity, retinal anatomy or other ocular findings should not be rescreened. Any rescreening request not mentioned here should be discussed with the study Medical Monitor. For rescreened subjects, imaging studies do not have to be repeated if performed in the 60 days prior to start of new screening. For rescreened subjects, clinical laboratory exams (bloodwork) do not have to be repeated if performed in the 45 days prior to start of the new screening.

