Laboratory data will be summarized by type of laboratory test. Reference ranges will be used in the summary of laboratory data. Frequency tabulations of the laboratory results will be presented in pre- versus posttreatment cross-tabulations (with classes for below, within, and above normal ranges) by treatment group. Frequency tabulations of the abnormalities by treatment group will also be made. A listing of subjects with any laboratory results outside the reference ranges will be provided.

Descriptive statistics will be calculated for each laboratory analyte at baseline and for observed values and changes from baseline at each scheduled time point by treatment group.

Vital Signs

Descriptive statistics of temperature, pulse/heart rate, respiratory rate, and blood pressure (systolic and diastolic) values and changes from baseline will be summarized at each scheduled time point by treatment group. The percentage of subjects with values outside standard reference ranges will be summarized by treatment group. A listing of subjects with any vital signs results outside the standard reference ranges will be provided.

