## 2.2. Baseline

For all assessments except for BCVA measurements (i.e., logMAR and total letters correct, both standard and low luminance), baseline will be defined as the most recent value prior to the Surgery Date (and time, if applicable). Thus the baseline could be derived based on Screening or Day 1 pre-op assessments or unscheduled pre-op assessments where applicable.

Baseline BCVA is assessed at an optional pre-screening visit (not recorded on the electronic case report form [eCRF] thus not used for analysis) and at the regular Screening visit (twice at that visit). For BCVA logMAR and total letters correct (both standard and low luminance), the better score at these 2 assessments will be used for baseline. For BCVA logMAR, a lower score is better. For total letters correct, a higher value is better.

Re-screening is allowed per protocol and the subject is not necessarily required to repeat every test during the 2nd screening. When a subject is re-screened, he/she receives a new subject ID. If a baseline value is not present for the current subject ID for this type of subject, it will be necessary to use the screening/baseline value captured in the 1st screening visit for that subject (captured using their previous subject ID) as the baseline value.

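### SAP 5.5 cannot count or flag a laboratory value that worsens from an already abnormal baseline, and it omits two laboratory tabulations that protocol 11.5 requires

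*SAP*

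**What the plan says.** **The rule.** For high results SAP 5.5 counts "those above the laboratory normal range where baseline was not above the normal range high value". For low results it says "TE abnormal low results are defined as those below the laboratory normal range where baseline was not below the normal range low value". These rules feed a frequency table per visit and an overall table of subjects with at least one such result. The listing shows every result but flags only the treatment-emergent ones.

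**Other laboratory output in the SAP.** SAP 5.5 also states "Descriptive statistics will be presented for each laboratory test at baseline and at each scheduled follow-up time point, and for the change from baseline". SAP 2 includes the minimum and maximum among the descriptive statistics.

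**The protocol.** Protocol 11.5 states "Frequency tabulations of the laboratory results will be presented in pre- versus posttreatment cross-tabulations", using three classes (below, within and above range). It separately asks for frequency tabulations of abnormalities, with no restriction to treatment-emergent ones, and for a listing of subjects with any out-of-range result.

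**Eligibility.** Protocol 4.2, exclusions 26 and 27, removes subjects with AST or ALT above 3x ULN, estimated creatinine clearance of 30 mL/min or less, or platelets below 100 x 10^3/uL. Milder abnormalities may enrol.

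**Neighbouring rules.** SAP 5 includes adverse events that worsened after baseline. The SAP 5.6 vital signs listing flags every value outside the reference range.

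**Rescreening.** Protocol 9.1.1.1 allows rescreening for, among other reasons, "decreased platelets and decreased renal function, if correctable with treatment or time", and says "clinical laboratory exams (bloodwork) do not have to be repeated if performed in the 45 days prior to start of the new screening". SAP 2.2 covers the case "If a baseline value is not present for the current subject ID for this type of subject" by going back to the first screening. Protocol Table 1, Note 1, says "Screening procedures must occur within 45 days prior to treatment and may occur over multiple days".

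**The concern.** A subject whose baseline is already out of range on one side can never meet the treatment-emergent definition on that side. Protocol 4.2 lets such subjects in, and they may have the least reserve. An adverse event that worsens is counted, but a laboratory value that worsens is not.

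The protocol's cross-tabulation would at least have shown how many subjects started out of range and where they ended. Its tabulation of all abnormalities would have included these subjects. Without either, a reader of the treatment-emergent table cannot tell a subject who stayed in range from one who could not have been counted. In a 21-subject safety study, each such subject is 1/21 = 4.8% of the cohort.

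**Working it through.** The plan states no figure for this point. SAP 1.4 gives no formula or error rate for the 21 subjects, so there is nothing to reproduce. The check applies the rules as written to test cases.

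**Step 1. The treatment-emergent rules.** High: value > ULN and baseline not > ULN. Low: value < LLN and baseline not < LLN. The documents give no platelet lower limit, so 130 to 150 x 10^3/uL is assumed; the result is the same across that range.

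| Test | Baseline | Post-baseline | Counted? |
|---|---|---|---|
| ALT (x ULN) | 0.9 | 1.1 | yes |
| ALT (x ULN) | 1.1 | 10 | no |
| ALT (x ULN) | 2.9 | 20 | no |
| Platelets (10^3/uL) | 160 | just below LLN | yes |
| Platelets (10^3/uL) | 105 | 20 | no |

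All of these baselines are admissible under exclusions 26 and 27.

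**Step 2. How likely such a baseline is.** Let p be the share of subjects out of range at baseline for a given test (assumed). The expected number is 21p, and the chance of at least one is 1 - (1 - p)^21.

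| p | Expected number of 21 | Chance of at least one |
|---|---|---|
| 2% | 0.4 | 0.35 |
| 5% | 1.1 | 0.66 |
| 10% | 2.1 | 0.89 |
| 20% | 4.2 | 0.99 |
| 30% | 6.3 | >0.99 |

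**Step 3. Denominator.** SAP 5.5 does not state one. Suppose 4 subjects become high and 3, 5 or 7 others were high at baseline (all assumed). Over the whole cohort the rate is 4/21 = 19.0%. Over subjects who could have the event it is 4/18 = 22.2%, 4/16 = 25.0% or 4/14 = 28.6%.

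**Step 4. What the remaining output shows.** A move from 2.9x to 10x ULN is a change of 10 - 2.9 = 7.1x ULN. It shifts the mean change by 7.1/21 = 0.34x ULN. It appears as the maximum change unless another subject rises more. The table therefore shows one extreme, but not how many subjects worsened or from what baseline.

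**Step 5. Whether the cross-tabulation alone is enough.** With three classes, 2.9x to 10x ULN falls in above-to-above, and so does a subject stable at 2.9x ULN. The cross-tabulation shows who started abnormal but does not separate worse from stable. A further criterion is needed. Crossing 3x ULN catches 2x to 10x, and crossing 100 x 10^3/uL catches platelets 105 to 20. Neither limit catches a rise from 1.1x to 2.9x ULN; graded multiples of the limit could.

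**Step 6. Rescreening.** Reused bloodwork may be up to 45 days old when the new screening starts, and that screening may last 45 days, so it could be 45 + 45 = 90 days old at surgery. Table 1, Note 1, allows 45. Table 1 schedules no routine laboratory test on Day 1 before surgery that would replace the old value.

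**The case against.** The strongest reply is that worsening is not hidden. SAP 5.5 keeps change from baseline for every test and scheduled visit, with extremes, and lists every result for 21 subjects. Protocol 9.5.2 has the investigator review each laboratory report and record clinically relevant changes as adverse events, where SAP 5 does include worsening. This stands against any claim that deterioration would be reported as zero: that is true of the treatment-emergent frequency table only. It does not supply a count. Adverse event recording rests on the investigator's judgement. Routine laboratory tests after surgery are scheduled only at Week 4 and Month 12, and under SAP 2.3 unscheduled results go to listings, where a worsened abnormal baseline carries no flag.

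A reader might also infer that a value that failed screening will serve as baseline. The documents read together do not support that. Protocol 9.1.1.1 allows rescreening for a correctable abnormality, and the note closing protocol 4.2 expects all criteria to be met at screening. A failed test would therefore be repeated, and SAP 2.2 would take the repeat as the most recent value. What remains is a wording gap: the reuse sentence makes no exception for the failed test, and other abnormal tests left unrepeated can carry over. Enrolment is closed, and the Amendment 2 log suggests that the rescreening text followed the first 21 subjects, so the gap may affect nobody. SAP 2.2 does provide for rescreened subjects, so this is not certain.

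A third tempting inference is that dropping the cross-tabulation causes the blind spot. Step 5 shows that it does not. The omission is a separate departure from the protocol.

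Finally, the primary objective concerns the surgical approach and Delivery System, nothing is tested formally, and the counts in Steps 2 and 3 are assumed. That limits the weight of the point but does not remove it, because safety of the cells is a major secondary objective.

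**Conclusion.** The point holds in a limited form and should be corrected.

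- The treatment-emergent rule cannot count or flag same-direction worsening from an out-of-range baseline, and eligibility admits such baselines. This follows from the text and needs no assumption.
- SAP 5.5 leaves out the protocol's cross-tabulation and its tabulation of all abnormalities, without a reason. Its flagging is narrower than that of SAP 5.6.
- The number affected is unknown. The 0.4 to 6.3 subjects per test, and the 19.0% against 22.2% to 28.6%, rest on assumed shares and counts and only illustrate the size.
- The documents do not support saying that deterioration would go unseen, or that a screen-failing value will normally be the baseline.

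**What to change.** In SAP 5.5:

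1. Restore the below/within/above cross-tabulation from protocol 11.5, as baseline by worst post-baseline value, and the tabulation of all abnormalities. For tests with two limits, show the lowest and highest values separately.
2. Add a count and a listing flag for worsening from an abnormal baseline. Graded multiples of the limit are one option. Crossing AST/ALT 3x ULN or platelets 100 x 10^3/uL, when not beyond it at baseline, is another. For renal function use serum creatinine: the panel in protocol 9.5.2 does not include clearance, and no estimating formula is given.
3. Give treatment-emergent percentages over subjects not abnormal in that direction at baseline, and state the denominator.
4. Flag every out-of-range value in the listing, as SAP 5.6 does for vital signs.

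A minor wording change belongs in SAP 2.2: where a test caused a screen failure, the later value that documented eligibility is the baseline. The bloodwork reuse text in protocol 9.1.1.1 and Table 1, Note 1, must be reconciled.

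The cost is SAP wording, a few extra table columns from data already collected, and some slightly less favourable percentages.

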#### 5.6. Vital Signs

Descriptive statistics of temperature, pulse/heart rate, respiratory rate, and blood pressure (systolic and diastolic) values and changes from baseline will be summarized at each scheduled time point.

Frequency tabulations of subjects with TE abnormal vital signs results will be presented for each test for each follow-up time point. TE abnormal low results are defined as those below the reference range value where baseline was not below the reference range low value. TE abnormal high results are defined as those above the reference range where baseline was not above the reference range high value. An overall tabulation will also be presented for subjects with at least 1 occurrence of a TE abnormal result at any follow-up time point for that test. A listing of subjects' vital signs results (all results at scheduled and unscheduled follow-up time points) will be provided, with flags for values outside the reference ranges.

Table 5: Vital Signs Reference Ranges				
Test	Reference Range Low	Reference Range High		
Temperature (C)	36	38		
Pulse (beats/min)	50	120		
Systolic Blood Pressure (mm HG)	90	180		
Diastolic Blood Pressure (mm HG)	50	105		

## 6. EFFICACY

## 6.1. BCVA

The primary efficacy measure will be the BCVA testing performed after refraction and under standardized photopic lighting conditions and distance using an ETDRS logMAR chart.

If the BCVA assessment was done, but total letters correct is missing because neither the 4m nor the 1m assessments could be done, (i.e., only highest degree of vision was done), the BCVA total letters correct will be assigned a value of 0 and BCVA logMAR score will be assigned a value of 1.7 (using the formula logMAR = 1.7 - [0.02 x total letters correct]).

Descriptive statistics will be presented for BCVA (letters and logMAR) at baseline and at each scheduled follow-up time point, and for the change from baseline, for the treated and fellow eye.

The count and percentage of BCVA responders at each follow-up time point (responder=yes for subjects who have BCVA change from baseline >=15 letters) will be summarized for the treated and fellow eye.

BCVA data for individual subjects will be presented in a data listing.

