1.1.2.2. Efficacy

Although Study CNTO2476RPG1001 was not designed as an efficacy study, secondary objectives included preliminary evaluations of changes from baseline in retinal structure and visual function. Overall, changes from baseline in visual acuity and retinal thickness were mixed. At the Month 3 visit, 3 subjects had measurable increases in retinal thickness in the treated eye, 3 subjects had decreases in retinal thickness, and 1 subject had no change from baseline values. The data were insufficient to make any meaningful conclusions. No durable changes in visual acuity were evident and data were variable. At 12 months post-treatment, no subject had any worsening of visual acuity. At the end of the study (Month 60), 3 subjects reported lower visual acuity (ie, no light perception or a shift from hand motion to light perception) at Month 12.

Study CNTO2476MDG1002, as described above, is currently ongoing and the efficacy results reflect combined data from both the Phase 1 and 2a portions of the study. At baseline, the median best corrected visual acuity (BCVA) for the 33 treated subjects was log of the minimum angle of resolution (logMAR) 1.2 (20/320) and logMAR 0.6 (20/80) in the treated eye and fellow eye, respectively. At 12 months post-treatment, median BCVA for 26 subjects was logMAR 1.1 (20/250) and logMAR 0.6 (20/80) in the treated eye and fellow eye, respectively, suggesting an improvement in BCVA in the treated eye compared with no change in the fellow eye. The mean change from baseline was 5 letters between fellow and treated eye at 6 months and 6.8 letters at 12 months.

BCVA gains and losses at 6 and 12 months post-treatment were as follows:

- At the 6-month assessment of BCVA gain, 10 subjects out of 27 (37%) had their treated eyes showing a ≥ 3 -line gain in BCVA. At the same time, 1 subject out of 27 (4%) had their fellow eyes showing a ≥ 3 -line gain in BCVA.
- At the 6-month assessment of BCVA loss, 6 subjects out of 27 (22%) had their treated eyes showing a ≥ 3 -line loss in BCVA. At the same time, 1 subject out of 27 (4%) had the fellow eye showing a ≥ 3 -line loss in BCVA.
- At the 12-month assessment of BCVA gain, 10 subjects out of 26 (39%) had their treated eyes showing a ≥ 3 -line gain in BCVA. At the same time, 1 subject out of 26 (4%) had their fellow eyes showing a ≥ 3 -line gain in BCVA.

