4.1. Inclusion Criteria

Each potential subject must satisfy all of the following criteria to be enrolled in the study.

1. Subject must be a man or woman at least 55 years to 90 years of age, inclusive.
- 2.2 Diagnosis of GA secondary to AMD confirmed within 45 days prior to initial randomization. Diagnosis verified by the central reading center using fundus photographs and including the following;

- The study eyes must have at least 1 GA lesion that involves the fovea, and a Macular Photocoagulation Study (MPS) disc areas (DA) of ≥ 0.5 and ≤ 7 (1 MPS disc area equivalent to 2.54 mm^2 on the retina) determined by screening images of fundus autofluorescence photographs as calculated by the reading center. If GA is multifocal, at least 1 lesion must be ≥ 0.5 DA.
 - In the Safety Run-in Phase only, DA of ≥ 0.5 with no maximum specified area, as long as the criteria below for photography can be met and the surgeon determines that the GA size will not impede cell delivery.
- Geographic atrophy must be able to be photographed in its entirety and may be contiguous with peripapillary atrophy.
- Retinal photographs, fundus autofluorescence images, and angiography of sufficient quality, allowing assessment of the macular area according to standard clinical practice, can be obtained.
- The imaging center must be able to delineate and confirm peripapillary atrophy with fundus photography and fundus autofluorescence.
- Images must include the central field 1, 2, and 3 field images as defined by the University of Wisconsin standards as well as a supero-temporal image to capture the subretinal injection area if possible.

- 3.2 Study eyes will have a BCVA of 20/80 to 20/800 (ETDRS logMAR value 0.6-1.6). The treatment eye will be that with the worse BCVA at screening. If BCVA is clinically equivalent, the eye with the larger GA determines the study eye.
4. Subject is a suitable candidate for ophthalmologic surgery, is willing and able to comply with the surgical procedure, scheduled visits, treatment plan, laboratory tests and other study procedures. Subject has met criteria of the surgery center anti-coagulation protocol, if applicable.
5. Female subjects must be post-menopausal with last menses 12 months prior, or longer, OR a measured follicle stimulating hormone $\geq 26 \text{ mIU/mL}$.

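### Every eye that cannot be tested on the chart is scored 0 letters, so a treated eye starting at 5 to 14 letters can never register a ≥15-letter loss, and no BCVA summary shows what vision remained

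*SAP*

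**What the plan says.** The rule in SAP 6.1 applies when "neither the 4m nor the 1m assessments could be done, (i.e., only highest degree of vision was done". In that case "the BCVA total letters correct will be assigned a value of 0 and BCVA logMAR score will be assigned a value of 1.7", by a conversion given as "using the formula logMAR = 1.7 - [0.02 x total letters correct" in square brackets. SAP 6.3 gives the same rule for low luminance BCVA. Neither section separates one level of off-chart vision from another.

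The planned output in SAP 6.1 is as follows:

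- Summary statistics, separately by eye: "Descriptive statistics will be presented for BCVA (letters and logMAR) at baseline and at each scheduled follow-up time point, and for the change from baseline".
- One categorical table: "The count and percentage of BCVA responders at each follow-up time point", where a responder is a gain of at least 15 letters.
- A by-subject listing of BCVA data. The SAP does not say whether the highest degree of vision is a field in it.

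The same letter score feeds two loss measures. SAP 5.3 defines significant loss of vision as a fall of at least 15 letters in the treated eye at Week 4 and gives it an exact binomial 95% interval. Protocol 9.2.2 lists the proportion losing at least 15 letters at 12 months as a major secondary endpoint.

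Protocol 4.1, criterion 3.2, sets the entry range: "Study eyes will have a BCVA of 20/80 to 20/800 (ETDRS logMAR value 0.6-1.6", both ends included. For the baseline value, SAP 2.2 says that "the better score at these 2 assessments will be used for baseline".

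**The concern.** The primary objective is the safety and performance of a new surgical approach and Delivery System. Protocol 3.2.4 justifies BCVA partly because it reflects harm as well as benefit. A severe loss of vision in the treated eye is the harm that such a measure should show most clearly.

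The rule replaces a recorded observation with a constant. Three consequences follow:

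- Eyes with different remaining vision become the same number.
- A further decline after an eye has reached 0 appears as no change, although BCVA is scheduled to Month 36 (Protocol Table 2).
- Where the baseline is already low, the score has too little room to fall for a 15-letter loss to be possible.

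The sponsor has treated off-chart levels as worth reporting before. For its retinitis pigmentosa study, Protocol 1.1.2.2 describes final vision in these terms: "3 subjects reported lower visual acuity (ie, no light perception or a shift from hand motion to light perception".

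**Working it through.** **Inputs.** Assigned score 0 letters / logMAR 1.7 and the conversion formula (SAP 6.1); eligible baseline logMAR 0.6 to 1.6 (Protocol 4.1); loss threshold 15 letters (SAP 5.3, Protocol 9.2.2); cohort of 21 (SAP 2.5); treated-eye median baseline of logMAR 1.2 in the earlier Phase 1/2a geographic atrophy study (Protocol 1.1.2.2).

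**Step 1: reproduce the plan's figure.** logMAR = 1.7 − 0.02 × 0 = 1.7. This agrees with the SAP.

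**Step 2: largest recordable loss.** Inverting the formula, letters = (1.7 − logMAR) / 0.02. Because the score stops at 0, the largest loss equals the baseline letters.

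| Baseline logMAR | Baseline letters = largest recordable loss | Can a ≥15-letter loss be recorded? |
|---|---|---|
| 0.6 | (1.7 − 0.6)/0.02 = 55 | yes |
| 1.2 | (1.7 − 1.2)/0.02 = 25 | yes |
| 1.4 | (1.7 − 1.4)/0.02 = 15 | yes, only just |
| 1.42 | (1.7 − 1.42)/0.02 = 14 | no |
| 1.6 | (1.7 − 1.6)/0.02 = 5 | no |

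Eligible eyes with 5 to 14 letters (logMAR 1.42 to 1.6) therefore cannot meet either loss measure. At the limit, complete loss of vision scores −5 letters, or +0.10 logMAR.

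**Step 3: effect on the mean.** With 21 eyes, one eye going from 5 to 0 letters moves the mean change by −5/21 = −0.24 letters. One going from 25 to 0 moves it by −25/21 = −1.19 letters. In neither case does the figure depend on what vision remains.

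**Step 4: effect on the Week 4 event.** Exact (Clopper–Pearson) 95% intervals, n = 21, assuming every subject has a Week 4 result. The number of affected eyes is not in the documents, so 0 to 2 is an assumed range.

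| Eyes starting at 5 to 14 letters that go off-chart (assumed) | As planned, no other events | If each were counted as a significant loss |
|---|---|---|
| 0 | 0/21: 0%, 0 to 16.1% | 0/21: 0%, 0 to 16.1% |
| 1 | 0/21: 0%, 0 to 16.1% | 1/21: 4.8%, 0.1 to 23.8% |
| 2 | 0/21: 0%, 0 to 16.1% | 2/21: 9.5%, 1.2 to 30.4% |

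For 0/21 the upper limit is 1 − 0.025^(1/21) = 0.161.

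**Step 5: does the rule reach the Week 4 event?** SAP 5.3 does not restate it. If the assigned 0 carries over, step 2 applies. If it does not, the off-chart eye has no letter score and cannot be counted either. An eye starting at 5 to 14 letters is missed on both readings.

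**The case against.** The strongest reply is that loss of vision has other routes into the tables. Protocol 9.5 requires clinically relevant changes to be recorded as adverse events, and Protocol 12.1.1 makes an event causing significant disability serious. SAP 5.1 tabulates ocular and serious ocular events by preferred term and affected eye. SAP 5.3 counts retinal detachment, choroidal haemorrhage, endophthalmitis and vitrectomy separately. This stands. A reader might infer that blindness after surgery would appear in no safety output; the documents do not support that. What remains is that these routes depend on an investigator's report and its coding, whereas the highest degree of vision is a scheduled measurement already recorded.

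A reader might also infer that blindness will generally look like a 5-letter loss. It will not. Five letters is the extreme case, at the eligibility limit. At logMAR 1.2 the same outcome scores −25 letters and, if present at Week 4, is counted as an event.

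The SAP does not list the levels of highest degree of vision. The protocol mentions hand motion, light perception and no light perception only for seven subjects with advanced retinitis pigmentosa, treated by a different route. It reports no off-chart level for the earlier geographic atrophy study. The proposed table must therefore use whatever categories the eCRF holds.

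The rule itself is defensible. Zero is the floor of the letter scale, 1.7 follows from the formula, and leaving these eyes missing would remove the worst results. No replacement score is proposed here.

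Finally, SAP 2 already provides the median, minimum and maximum, and there is a listing. A minimum of 0 shows that at least one eye is at the floor. It does not show how many, or what vision they have.

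**Conclusion.** The concern holds within limits. The masking lies in the BCVA and low luminance BCVA summaries and in the two ≥15-letter-loss measures, not in all safety output. For treated eyes starting at 5 to 14 letters it is complete for the loss measures. For eyes starting at 15 letters or more, the loss is counted, but the remaining vision is not shown.

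Its practical size depends on how many of the 21 treated eyes started below 15 letters and went off-chart, and the documents give neither number. Low baselines are plausible, since the eye with the worse vision is treated and the earlier geographic atrophy study had a treated-eye median of logMAR 1.2. That is not evidence that any enrolled eye was affected. If one was, the Week 4 result changes from 0/21 to 1/21. The study is descriptive, so no test or error rate is affected. This is an inexpensive improvement in reporting that should be made, not a flaw that invalidates the analysis.

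**What to change.** Keep the assigned 0 letters / logMAR 1.7 and make three additions to the SAP:

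1. Add one table by eye and visit showing the number of eyes with letters read and the number in each highest-degree-of-vision category as recorded in the eCRF, with shift from baseline. Name that field as part of the BCVA listing.
2. Print the number of assigned zeros beside each BCVA and low luminance BCVA mean.
3. Beside the Week 4 and 12-month ≥15-letter-loss counts, state how many treated eyes had a baseline below 15 letters and how many of those went off-chart. SAP 6.1 tabulates only gains of at least 15 letters, so the 12-month loss count itself has to be added for this note to attach to.

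The cost is one more output and two footnotes, apart from the 12-month loss count that Protocol 9.2.2 already calls for. It uses data already recorded and changes no visit, assessment or procedure.
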